**11.2.4. Immunogenicity**

- For a given subject and given immunogenicity measurement, missing or non-evaluatable measurements will not be replaced. Therefore, an analysis will exclude subjects with missing or non-evaluatable measurements.
- The Geometric Mean Concentrations (GMC) calculations are performed by taking the anti-log of the mean of the log concentration transformations. Antibody concentration below the cut-off of the assay will be given an arbitrary value of half the cut-off of the assay for the purpose of GMC calculation. Antibody concentration above the assay cut-off (i.e. the ELISA upper limit of quantification) will be given twice the cut-off value.
- A seronegative subject is a subject whose antibody concentration is below the cut-off value of the assay. A seropositive subject is a subject whose antibody concentration is greater than or equal to the cut-off value of the assay.
- All CIs computed will be two-sided 95% CIs.

**CONFIDENTIAL**207759 (NTHI MCAT-008)  
Statistical Analysis Plan Amendment 1 Final**11.2.5. Safety**

Solicited adverse event: with the exception of 60 minutes after vaccination, solicited adverse events are collected via paper-diary and thus no DCF (data clarification form) will apply in case of inconsistency reporting.

For a given subject and the analysis of solicited symptoms within 7 days post-vaccination, missing or non-evaluable measurements will not be replaced. Therefore the analysis of the solicited symptoms based on the Solicited Safety Set will include only vaccinated subjects for doses with documented safety data (i.e., symptom screen completed). More specifically the following rules will be used:

- subjects who documented the absence of a solicited symptom after one dose will be considered not having that symptom after that dose;
- subjects who reported solicited safety data at a visit, but they didn't report any daily measurement for a certain symptom, they will be counted as missing for that symptom at that visit;
- subjects who documented the presence of a solicited symptom and fully or partially recorded daily measurement over the solicited period will be included in the summaries at that dose and classified according to their maximum observed daily recording over the solicited period;
- doses without symptom sheets documented will be excluded;
- the duration of solicited adverse events will be calculated as the sum of the consecutive days with the symptom reported at Grade 1 or higher. The duration of solicited events at a specific grade (e.g., Grade 3) will be calculated as the sum of the consecutive days with the symptom reported at that grade. The same rule applies for solicited adverse events ongoing at the end of the solicited follow-up period considering the maximum intensity reported;
- when the occurrences of solicited adverse events are summarised, each event recorded as having occurred during a specific period will be counted as the number of occurrences the event is consecutively reported (at Grade 1 or higher);
- when the occurrences of solicited adverse events at a specific grade are summarised, each event recorded as having occurred at that grade during a specific period will be counted as the number of occurrences the event is consecutively reported at that grade.

For analysis of unsolicited adverse events, such as serious adverse events or adverse events by primary MedDRA term, and for the analysis of concomitant medications, all vaccinated subjects will be considered. Subjects who did not report the event or the concomitant medication will be considered as subjects without the event or the concomitant medication respectively. Note that for all tables described in this section, the way the percentage of subjects will be derived will depend on the event analysed (see table below for details). As a result, the N value will differ from one table to another.

**CONFIDENTIAL**207759 (NTHI MCAT-008)  
Statistical Analysis Plan Amendment 1 Final

Event	N used for deriving % per subject for Vaccination phase	N used for deriving % per dose for Vaccination phase
Concomitant vaccination	All subjects with study vaccine administered	
Solicited local/general symptom	All subjects, with study vaccine administered, with at least one solicited symptom, either local or general, documented as either present or absent (i.e., symptom screen completed)	All study visits with study vaccine administered and with at least one solicited symptom, either local or general, documented as either present or absent (i.e., symptom screen completed)
Unsolicited symptom with onset within 30 days	All subjects, with study vaccine administered, that have safety data	
Unsolicited symptom (e.g., SAEs, AEs leading to withdrawal,..)	All subjects with study vaccine administered	
Concomitant medication	All subjects with study vaccine administered	

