**Immunogenicity**

- Calculation of the GMCs will be performed by taking the anti-logarithm in base 10 (anti-log10) of the mean of the log10 concentration transformations.
- Antibody concentrations below the assay cut-off will be given an arbitrary value of half the assay cut-off for the purpose of geometric mean concentration (GMC) calculation.
- A seronegative subject is defined as a subject whose antibody concentration is below the assay cut-off value (i.e. the ELISA lower limit of quantification).
- A seropositive subject is defined as a subject whose antibody concentration is greater than or equal to the assay cut-off value (i.e. the ELISA lower limit of quantification).
- For a given subject and the analysis of a given immunogenicity measurement, missing or unevaluable measurements will not be replaced.

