**6.4. Immunogenicity****6.4.1. Analysis of immunogenicity planned in the protocol**

The analysis will be performed on the PPS at first line. If the percentage of vaccinated subjects with serological results excluded from the PPS is more than 10%, a second line analysis will be performed on the FAS.

The CMI analysis will be performed on the FAS – CMI Subset.

**CONFIDENTIAL**207759 (NTHI MCAT-008)  
Statistical Analysis Plan Amendment 1 Final**6.4.1.1. Humoral Immunogenicity****6.4.1.1.1. Within groups assessment****ELISA**

For each group, eight timepoints (Day 1, Day 91, Day 181, Day 211, Day 361, Day 391, Day 541 and Day 721, when blood samples are collected) are considered for humoral immune response against the four antigens PD, PE, PilA and UspA2, for which the following will be computed:

- Seropositivity rate and associated 95% CI at each time point (See Additional considerations for seroresponse definition and assay cut-off values).
- GMCs at each time point and their 95% CIs.

With respect to antibody levels at Day 1 (before 1st dose):

- GMRs at each time point and their 95% CIs.
- Percentage of subjects with 2-fold, 4-fold and 8-fold increase at each time point and associated 95% CI.

With respect to antibody levels at Day 181 (before 3rd dose):

- GMRs at Day 211, Day 361, Day 391, Day 541 and Day 721 and their 95% CIs.
- Percentage of subjects with 2-fold, 4-fold and 8-fold increase at Day 211, Day 361, Day 391, Day 541 and Day 721 and associated 95% CI.

With respect to antibody levels at Day 361 (before 4th dose):

- GMRs at Day 391, Day 541 and Day 721 and their 95% CIs.
- Percentage of subjects with 2-fold, 4-fold and 8-fold increase at Day 391, Day 541 and Day 721 and associated 95% CI.

The distribution of antibody concentrations will be displayed using Reverse Cumulative Curves.

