**6.4.1.1.2. Between groups assessment**

Comparative analyses will be exploratory with the aim to characterise the difference between groups in humoral immune response.

At each visit, the group difference in terms of GMCs and GMRs (except at Day 361) will be evaluated, by computing GMC and GMR ratio, between the two groups, and their associated two-sided 95% CIs.

Differences in percentages of subjects with ELISA concentration > 'Assay cut-off' between the groups will be also calculated with the associated two-sided 95% CIs.

**CONFIDENTIAL**207759 (NTHI MCAT-008)  
Statistical Analysis Plan Amendment 1 Final**6.4.1.2. Cell-mediated immune response**

CMI induced by the NTHi-Mcat candidate vaccine will be evaluated presenting the frequencies (including mean, medium, minimum and maximum) of antigen-specific CD4+ /CD8+ T cells per 10^6 cells. The specific CD4+ / CD8+ T cells being identified as the CD4+ / CD8+ T cells expressing at least 2 different cytokines/activation markers among CD40 Ligand (CD40L), IL-2, TNF- $\alpha$ , IFN- $\gamma$ , IL-13 and IL-17 upon *in vitro* stimulation will also be evaluated. Descriptive statistics (Min, Q1, Median, Q3 & Max) will be reported for each group at Day 1, Day 91, Day 181, Day 211, Day 361 and Day 391.

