**6.4.2. Additional considerations****6.4.2.1. Humoral Immunogenicity**

- Calculation of the GMCs will be performed by taking the anti-logarithm in base 10 (anti-log10) of the mean of the log10 ELISA concentration.
- Antibody concentrations below the assay cut-off will be given an arbitrary value of half the assay cut-off for the purpose of geometric mean concentration (GMC) calculation.
- A seronegative subject is defined as a subject whose antibody concentration is below the assay cut-off value (i.e. the ELISA lower limit of quantification). Specifically, the assay cut-off values are defined as follows:

*Anti-PD antibodies: 153 EU/mL*

*Anti-PE antibodies: 16 EU/mL*

*Anti-PilA antibodies: 8 EU/mL*

*Anti-UspA2 antibodies: 28 EU/mL*

Assay cut-off and unit might be subject to change during the study (e.g. in case of assay re-optimization, qualification, (re)validation or standardization). In this case, this will be documented in the clinical study report.

- A seropositive subject is defined as a subject whose antibody concentration is greater than or equal to the assay cut-off value (i.e. the ELISA lower limit of quantification).
- For a given subject and analysis of a given immunogenicity measurement, missing or unevaluable measurements will not be replaced.

**CONFIDENTIAL**207759 (NTHI MCAT-008)  
Statistical Analysis Plan Amendment 1 Final

- The percentage of seropositive subjects and associated two-sided 95% Clopper-Pearson [1] confidence intervals (CIs) will be computed by vaccine group at each visit.
- The 95% CIs for the difference between the percentages of seropositive subjects will be computed using Miettinen and Nurminen method [2] which has superior performance characteristics when rates are close to 0 or close to 1 and when compared to those formed from the Wald statistic.
- GMCs for each group and their ratios at each post-exposure timepoint will be calculated by fitting an ANCOVA model including the country, age category (40 - 59 years or 60 - 80 years) and smoking status (current or former smokers) as factors and pre-Dose 1 concentration (as covariate).

The SAS statements that will be used to calculate the adjusted GMC will be similar to:

```
PROC glm;
  BY timepoint antibody;
  CLASS country age smoking_status group;
  MODEL logtiter= log_baseline country age smoking_status group;
  LSMEANS group / tdiff stderr cl pdiff;
RUN;
```

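### Does the loosely worded rule for ELISA results above the upper limit of quantification in SAP 11.2.4 need correcting?

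*SAP*

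**What the plan says.** SAP 11.2.4 gives two substitution rules in its bullet on calculating GMCs. A result below the cut-off "will be given an arbitrary value of half the cut-off of the assay for the purpose of GMC calculation". The sentence after that covers high results: "Antibody concentration above the assay cut-off (i.e. the ELISA upper limit of quantification) will be given twice the cut-off value". The next bullet returns to the lower-limit meaning: "A seropositive subject is a subject whose antibody concentration is greater than or equal to the cut-off value of the assay".

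SAP 6.4.2.1 ties the term to the lower limit: "A seronegative subject is defined as a subject whose antibody concentration is below the assay cut-off value (i.e. the ELISA lower limit of quantification"). It lists the values as 153 (PD), 16 (PE), 8 (PilA) and 28 (UspA2) EU/mL, and protocol Table 8 and Appendix A agree. Protocol 10.6 has the low-result rule only: "Antibody concentrations below the assay cut-off will be given an arbitrary value of half the assay cut-off". Neither protocol 10.6 nor SAP 6.4.2.1 has a rule for high results, so SAP 11.2.4 is the only source.

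The outputs that could be affected are in SAP 6.4.1.1.1 and 6.4.2.1: GMCs, GMRs and, against Day 1, "Percentage of subjects with 2-fold, 4-fold and 8-fold increase at each time point and associated 95% CI", with similar rates against Day 181 and Day 361. The GMC model is "MODEL logtiter= log_baseline country age smoking_status group". On comparing the arms, SAP 6.4.1.1.2 says: "Comparative analyses will be exploratory with the aim to characterise the difference between groups in humoral immune response".

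**The concern.** Three things look wrong. One term names both ends of the assay range within a few lines. The text tells the programmer to double a limit but prints no number for it. And the low-result rule is confined to GMCs in so many words while the high-result rule is not, so it could be carried into the GMRs, the fold-rise rates and the baseline covariate.

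If it were, single calls could go either way. Write U for the ULOQ. A subject going from 0.9U to 1.2U has a true rise of 1.2/0.9 = 1.33 but is recorded at 2/0.9 = 2.22, a false 2-fold responder. A subject going from 0.6U to 3U has a true rise of 5.0 but is recorded at 2/0.6 = 3.33, a missed 4-fold responder. If both values exceed U, the recorded ratio is 1 whatever happened.

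These outputs describe the response to the third vaccine dose. At Day 211 only Schedule 1 has had it, and at Day 391 Schedule 2 is one month past its own. The share above U could therefore differ between arms, so a poor rule could distort the comparison.

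**Working it through.** **1. Which limit is meant?** Try the literal reading, with the listed cut-offs as the number to double. Every result above the lower limit would become 2 × 153 = 306 (PD), 2 × 16 = 32 (PE), 2 × 8 = 16 (PilA) or 2 × 28 = 56 (UspA2) EU/mL. With c/2 for low results, the largest possible fold rise would be 2c ÷ (c/2) = 4. The planned 8-fold rates would then be zero by construction and the reverse cumulative curves empty of information. No analyst would program that, and the parenthesis in the sentence names the upper limit.

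**2. Is doubling the upper limit a poor rule for GMCs?** Assume log10 concentrations are normal with standard deviation s and that a share f lies above U. Neither is given for this purpose. I take f = 5%, 10% and 20%, and s = 0.3, 0.5 and 0.83. The last is the standard deviation in protocol 10.4, whose scale is not stated.

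Let z = Φ⁻¹(1 − f). The mean log10 excess above U is e = s × (φ(z)/f − z). Then:

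- GMC with 2U ÷ true GMC = 10^[f × (0.301 − e)]
- GMC with U ÷ true GMC = 10^(−f × e)

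Example, f = 20% and s = 0.3: z = 0.842, φ(z) = 0.280, φ(z)/f − z = 0.558, e = 0.167. With 2U: 10^(0.2 × 0.134) = 1.063. With U: 10^(−0.2 × 0.167) = 0.926.

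| f | 2U: s = 0.3 / 0.5 / 0.83 | U: s = 0.3 / 0.5 / 0.83 |
|---|---|---|
| 5% | 1.020 / 1.011 / 0.995 | 0.986 / 0.976 / 0.961 |
| 10% | 1.037 / 1.015 / 0.979 | 0.968 / 0.947 / 0.914 |
| 20% | 1.063 / 1.010 / 0.928 | 0.926 / 0.879 / 0.808 |

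The 2U rule is exact where e = 0.301, at s = 0.72, 0.64 and 0.54 for f = 5%, 10% and 20%. Its error therefore changes sign inside the assumed range. U is slightly closer only at s = 0.3 with f of 5% or 10%; in the other seven cells 2U is closer.

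**3. Between arms.** With 20% above U in one arm and 5% in the other, the GMC ratio is multiplied by 1.063/1.020 = 1.042 at s = 0.3, and by 0.999 and 0.933 at s = 0.5 and 0.83. With U the factors are 0.939, 0.901 and 0.841. A simulated ANCOVA with 90 per arm (baseline correlation 0.6, 1,500 runs) gave 1.047, 0.995 and 0.929 for 2U. A censored-normal model gave 1.004, 0.995 and 0.996.

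**4. Fold-rise rates, if the rule covers them.** Simulation over 18 scenarios per f: reference log10 SD 0.3, 0.5 or 0.83; median rise 1.5, 2 or 4; log10 SD of the rise 0.2 or 0.4; one million subjects each. Error of the rate in percentage points, 2U minus truth:

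| f | 2-fold | 4-fold | 8-fold |
|---|---|---|---|
| 5% | −0.7 to +0.9 | −0.5 to +1.7 | −0.3 to +1.7 |
| 10% | −1.8 to +1.9 | −1.4 to +2.9 | −0.9 to +3.0 |
| 20% | −5.0 to +3.6 | −3.8 to +4.4 | −2.6 to +4.5 |

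The median absolute error is 1.3 points or less throughout. False 2-fold calls reach at most 2.4% of subjects at f = 10% and 5.1% at 20%, in the scenarios with a median rise of 1.5 or 2. With a median rise of 4 the maxima fall to 0.2% and 0.4%. Counting only certain responders, which is the same as assigning U, understates the rates by up to 4.7 points at f = 10% and 10.3 at 20%.

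**The case for a change.** The best case for acting is that a few words would cure this: separate names for the two limits, the ULOQ for each antigen, a line on which outputs take substituted values, and a count of results above the limit by group, antigen and visit. That would remove discretion before anyone sees results. A censored-normal sensitivity analysis would also recover the arm ratio better than 2U if over-range results were common and unequal.

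The textual part stands: the term is misused, the number is absent and the scope is unstated. The wording would be tidier with those few lines. But they record choices a competent analyst would make anyway. The gap is also not peculiar to the upper end, since the plan is equally silent on how results below the lower limit enter the GMRs and fold-rise rates.

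The heavier additions are a matter of preference. The censored model relies on log-normality. For GMRs it sets aside subjects whose reference value is already above U, which can shift the estimate if the rise depends on the starting level. Fold-rise bounds are wide when many results are censored. For secondary summaries and exploratory comparisons, statisticians could reasonably decline both.

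**Conclusion.** No change to the plan follows. The naming is a clerical slip that the sentence itself corrects. The missing ULOQ and scope are a gap that analysts can fill sensibly from the laboratory's assay limits and the sentence's place in the GMC bullet. The substitution is not shown to be wrong: it moves the GMC by at most about 4% at f = 10%, can err in either direction, and is usually closer to the truth than assigning the ULOQ.

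The fold-rise errors arise only if the rule is extended to those rates, and they are typically about one percentage point or less. The largest figures need 20% of results above the limit, for which the documents offer no support. The effect is zero if no sample exceeds the limit.

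The sizes rest on log-normal concentrations and on assumed values of f, s and the distribution of rises. The primary safety results do not depend on any of this.

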**Potential immune mediated diseases (pIMD).**

pIMDs are a subset of AEs that include autoimmune diseases and other inflammatory and/or neurologic disorders of interest which may or may not have an autoimmune aetiology. The investigator will exercise his/her medical and scientific judgement in deciding whether other diseases have an autoimmune origin (i.e. pathophysiology involving systemic or organ-specific pathogenic autoantibodies) and should also be recorded as a pIMD. In order to facilitate the documentation of pIMDs in the eCRF a pIMD standard questionnaire and a list of preferred terms (PTs) and PT codes corresponding to the above diagnoses will be available to investigators at study start.

**12. ANNEX 2: NUMBER OF DECIMALS DISPLAYED**

The following decimal description from the decision rules will be used for the demography, immunogenicity and safety/reactogenicity.

Display Table	Parameters	Number of decimal digits
Demographic characteristics	Mean, median age	1
Demographic characteristics	SD (age)	1
Immunogenicity	Ratio of GMT/C	2
Reactogenicity	Mean, Min, Q1, Median, Q3, Max for duration	1
All summaries	% of count, including LL & UL of CI	1
All summaries	% of difference, including LL & UL of CI	2
All summaries	p-value	3

**LIST OF ABBREVIATIONS**

[figure not shown]
AE	Adverse event
AESI	Adverse Events of Special Interest
ANCOVA	Analysis of Covariance
ANOVA	Analysis of Variance
CI	Confidence Interval
CRF	Case Report Form
CSR	Clinical Study Report
CTRS	Clinical Trial Registry Summary
EL.U/ml	ELISA unit per milliliter
Eli Type	Internal GSK database code for type of elimination code
ELISA	Enzyme-linked immunosorbent assay
ES	Exposed Set
FAS	Full Analysis Set
GMC	Geometric mean antibody concentration
GMT	Geometric mean antibody titer
GSK	GlaxoSmithKline
IU/ml	International units per milliliter
LL	Lower Limit of the confidence interval
MedDRA	Medical Dictionary for Regulatory Activities
N.A.	Not Applicable
PCD	Primary Completion Date
PD	Protocol Deviation
PPS	Per Protocol Set
SAE	Serious adverse event
SAP	Statistical Analysis Plan
SBIR	GSK Biological's Internet Randomization System
SD	Standard Deviation
SR	Study Report
TFL	Tables Figures and Listings
TOC	Table of Content
UL	Upper Limit of the confidence interval
WBR	Web-based Randomization

# 1. DOCUMENT HISTORY

Date	Description	Protocol Version
05-MAR-2018	Final version	Final – 28-JULY-2017

# 2. STUDY DESIGN

Figure 1 Study design overview

BS H = blood sample for humoral immune responses  
 BS C = blood sample for cellular immune responses from 20% of subjects in each group  
 Rando = randomisation; V = Visit; D = Day; Vacc = vaccination (indicated in grey)  
 Vaccine = 10-10-3-AS formulation; Pbo = Placebo; FU = Follow-up; PC = Phone contact

- **Experimental design:** Phase II, observer-blind, randomised, multi-centric study with two parallel groups.
- **Duration of the study:** for each subject enrolled, the study will last approximately 2 years from Visit 1 (enrolment visit):
  - Epoch 001 : Primary (Vaccination phase) starting at Visit 1 (Day 1) and ending at Visit 9 (Day 541).
  - Epoch 002 : Long-term follow-up starting after Visit 9 (Day 541) and ending at Visit 10 (Day 721).
- Primary Completion Date (PCD): Visit 9 (Day 541).

Refer to the Glossary of terms of the protocol for the definition of PCD.

- **End of Study (EoS):** Last testing results released of samples collected at Visit 10 (Day 721).

Refer to the Glossary of terms of the protocol for the definition of EoS.

- Study groups:
  - **Schedule 1** : Approximately 100 subjects receiving three doses of the AS01E-adjuvanted GSK Biologicals' NTHi-Mcat investigational vaccine containing 10 µg of PD, 10 µg of PE-PilA, and 3.3 µg of UspA2 at Visit 1 (Day 1), Visit 3 (Day 61) and Visit 5 (Day 181) and one dose of placebo at Visit 7 (Day 361).
  - **Schedule 2** : Approximately 100 subjects receiving three doses of the AS01E-adjuvanted GSK Biologicals' NTHi-Mcat investigational vaccine containing 10 µg of PD, 10 µg of PE-PilA, and 3.3 µg of UspA2 at Visit 1 (Day 1), Visit 3 (Day 61) and Visit 7 (Day 361) and one dose of placebo at Visit 5 (Day 181).

**Table 1 Study groups and epochs foreseen in the study**

Study groups	Number of subjects	Age (Min/Max)	Epochs	
			Epoch 001	Epoch 002
Schedule 1	100	40 – 80 years	x	x
Schedule 2	100	40 – 80 years	x	x

**Table 2 Study groups and treatment foreseen in the study**

Treatment name	Vaccine/Product name	Study Groups	
		Schedule 1	Schedule 2
10-10-3/AS01E	NTHi-Mcat 10-10-3	x	x
	AS01E	x	x
Placebo	Formulation buffer S9b	x	x

- **Vaccination schedule:** at Visit 1 (Day 1), Visit 3 (Day 61), Visit 5 (Day 181) and Visit 7 (Day 361).
- **Treatment allocation:** Subjects will be allocated to a study group using a centralised randomisation system on internet (SBIR).
- **Blinding:** observer-blind (Epoch 001) and open (Epoch 002).

